6.3.6 Compliance to Treatment

Compliance to AG019 and teplizumab will be calculated, separately.

All patients in the repeat dose cohorts, and all patients in the combination cohorts who are randomized to study treatment, were planned to be treated for 8 weeks (56 days) with either 2 or 6 capsules (low or high dose) of AG019.

All patients in the combination cohorts were planned to be treated for 12 days with teplizumab or teplizumab placebo (daily IV infusions for at least 30 minutes) in addition to their AG019/placebo treatment.

Each patient was instructed to return all used and unused study drug at each visit during the active treatment period and at the end of the treatment phase. A count of the used and unused capsules was performed to assess compliance. Teplizumab (or corresponding placebo) accountability and compliance were verified at every follow-up visit by the site staff.

AG019 compliance will be calculated as the percentage of total doses received / total planned doses that were actually taken x 100. For single dose patients the planned total doses were 2 or 6 capsules. For patients in the repeat cohorts dosed with 2 capsules/day the total planned amount was 112 capsules. For patients in the repeat cohorts dosed with 6 capsules/day and patients in the combination cohorts (which were also dosed with 6 capsules/day) the total planned amount was 336 capsules.

Teplizumab compliance will be calculated as the percentage of days teplizumab infusion was given of the planned 12 days. Incomplete infusions will be calculated as given for that day.

Compliance to AG019 and teplizumab will be tabulated with summary statistics for the safety set. All individual data will be listed.

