If, at any time during the study, safety concerns associated with the high dose of AG019 are identified, the DSMB will recommend lowering the daily dose of AG019 in all ongoing and planned AG019 cohorts, as well as in all ongoing and planned combination cohorts.

XXX

5.1.2Teplizumab

All patients in the combination cohorts who are randomized to study treatment, as well as the first 2 patients in the combination cohorts who are treated in open label, will be treated for 12 days with teplizumab (daily IV infusions) according to the below schedule, in addition to their AG019 treatment:

XXX			

XXX

The parameters used to calculate the daily dosing of study drug will be based on the height and weight at Day 1. The total cumulative average dose will be 9034 μ g/m² or approximately ~17 mg for each patient. This total dose is the same as that used in previous trials in a 14 day regimen (Sherry et al., 2011; Hagopian et al., 2013; Herold et al., 2013; Herold et al., 2013) with the change that the protocol

Confidentiality Statement

has been shortened XXX

5.1.3T1D therapy during the study

During the study, all patients will receive appropriate diabetic therapy according to current ADA or equivalent guidelines. Treatment with commercially available insulin (multiple dose insulin injection therapy, continuous subcutaneous insulin infusion therapy or analogue therapies) is allowed. Treatment with other forms of commercially available insulin therapy, or treatment with experimental insulin, is not allowed during this study.

In accordance with ADA recommendations, preprandial glucose level target should be 4.4-7.2 mmol/L (80-130 mg/dL) and peak post prandial (1-2h after meal) glucose level target should be <10 mmol/L (<180 mg/dL).

5.1.40ther concomitant therapy

Any concomitant therapy used by the patient at any time following ICF signature must be recorded in the eCRF through the end of the short term follow-up must be recorded on the eCRF. In addition, for any SAEs that require medication for treatment, those medications must be recorded on the concomitant medications page. The medication name, dosage, frequency, route of administration, start and stop dates, and indication for use must be recorded. The medical monitor should be notified in advance of (or as soon as possible after) any instances in which prohibited therapies are administered. The MM will subsequently advise on actions to be taken, if any.

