10.3. Definitions of Study Populations for Analysis

10.3.1The Safety (SAF) Analysis Set

The safety population will include all patients who receive at least one dose of study medication. Only patients with clear documentation that no study medication was received may be excluded from analysis. Patients will be analyzed according to the dose received. This population will be used for all data summaries.

10.3.2The Pharmacokinetic (PK) Analysis Set

For each cohort, all patients who received the IMP as scheduled and provided sufficient samples to reliably estimate the PK parameters will be included in the PK analysis set.

More details on the PK parameters, analysis and presentation of study results will be provided in the SAP.

10.3.3The Pharmacodynamic (PD) Analysis Set

For each cohort, all patients who received the IMP as scheduled and provided sufficient samples to reliably estimate the PD parameters will be included in the PD analysis set.

More details on the PD parameters, analysis and presentation of study results will be provided in the SAP.

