5 DATA SETS TO BE ANALYZED

The following analysis sets will be used for the statistical analysis and presentation of data:

- **The Safety (SAF) Analysis Set.** The safety population will include all patients who received at least one dose of AG019. Only patients with clear documentation that no study medication was received may be excluded from analysis. Patients will be analyzed according to dose received. This population will be used for all data summaries.
- **The Pharmacodynamic Intention To Treat (PD-ITT) Analysis Set.** All patients in the repeat dose and combination cohorts who received at least one dose of AG019 will be included in the PD-ITT analysis set.
- **The Pharmacodynamic Per Protocol (PD-PP) Analysis Set.** All data from patients in the repeat dose and combination cohorts who received at least 75% of the scheduled doses of AG019* and at least one dose of teplizumab in the combination cohorts and had no major protocol deviations affecting the main PD endpoints at the time point of data collection** will be included in the PD-PP analysis set.

* XXXXXXXXXXXXXXXXXXXXXXX

** XXXXXXXXXXXXXXXXXXXXXXX

All patients to be included in the PD-ITT and PD-PP Analysis sets will be determined before data base lock. The Safety Set is considered the primary analysis dataset, and will be used for safety presentations and all other data summaries (except for PD summaries). All summaries will be performed according to dose received. Baseline presentations will be based on the safety set.

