If the start date of an AE is missing, it will be assumed that the AE started after the first administration of IMP. If the start date of an AE is partially missing, and it has started the same year and/or month as the IMP it will be assumed that the AE started after the first administration of IMP. If an AE occurred on the same day as dosing but the onset time is missing the AE will be assumed to be a TEAE.

The infusion of teplizumab was considered withheld if the answer to the CRF question 'Was the Teplizumab infusion given?' was 'No, infusion not started' and/or if the answer on the AE page on 'Action Taken With Study Treatment Teplizumab' was 'Drug interrupted' or 'Drug withdrawn'.

Study treatment of AG019 was considered discontinued if the answer to the CRF question "Action Taken with Study Treatment AG019" was "Drug interrupted" or "Drug withdrawn".

A summary table per cohort will present number of TEAEs, number of unique TEAEs (counted once within each subject at the preferred term level) and number of subjects with at least one event for TEAEs, SAEs, related TEAEs, TEAEs leading to discontinuation of IMP/withdrawal and more.

Tables with

- All AEs by System Organ Class (SOC) and PT,
- All TEAEs by SOC and PT, in total and for the AG019 treatment period only,
- All TEAEs by SOC and PT according to severity, in total and for the AG019 treatment period only,
- All TEAEs by SOC and PT according to relatedness, in total and for the AG019 treatment period only,
- All serious TEAEs by SOC and PT,

will be given. If there are no events an empty table will be produced.

All AEs will be listed. In addition all TEAEs leading to AG019 treatment discontinuation and study infusion withholding will be listed.

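### Teplizumab compliance credits incomplete infusions in full, and the per-protocol PD set asks for only one teplizumab dose against 75% of AG019 doses

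*SAP*

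**What the plan says.** **Exposure.** Protocol 5.1.2 plans 12 daily infusions scaled to body size: "The total cumulative average dose will be 9034" µg/m². Protocol 11.4.3.5.1 does not lengthen the course past day 12 when days are lost. SAP 6.3.6 defines the measure: "Teplizumab compliance will be calculated as the percentage of days teplizumab infusion was given of the planned 12 days". The next sentence is "Incomplete infusions will be calculated as given for that day". Section 7.1 of the SAP lists one teplizumab compliance table, and 6.3.6 promises individual listings. No output is specified for the amount delivered.

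**Withheld infusions.** SAP 6.3.8 sets a different rule for adverse event reporting: "The infusion of teplizumab was considered withheld if the answer to the CRF question" was that it had not been started, and/or the AE page recorded teplizumab as interrupted or withdrawn.

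**Per-protocol PD set.** SAP 5 admits patients who "received at least 75% of the scheduled doses of AG019* and at least one dose of teplizumab in the combination cohorts" and who "had no major protocol deviations affecting the main PD endpoints at the time point of data collection". Two footnotes, one on the AG019 rule and one on the deviation clause, are redacted. Protocol 10.3.3 defines the PD set as "all patients who received the IMP as scheduled and provided sufficient samples to reliably estimate the PD parameters". SAP 6.1 states that the planned analyses have not changed.

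**The concern.** The trial's primary objective covers the tolerability of AG019 given with teplizumab, so a reader needs to know how much teplizumab was given. A day count that treats a stopped infusion like a finished one cannot show that, and the stopped infusion is credited upward every time. If the AE section classes the same infusion as withheld, two outputs in one report could disagree about one event.

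The per-protocol rule raises a different question. It sets a demanding bar for one component of the combination and a nominal one for the other. A patient with 1/12 of the planned infusions can sit in a set whose name suggests treatment close to plan. At stake are the exposure table and the descriptive summaries of HbA1c, insulin-dose-adjusted HbA1c and insulin dose.

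**Working it through.** The plan gives no delivered-dose figure to reproduce. The capsule totals in SAP 6.3.6 do reproduce: 2 × 56 = 112 and 6 × 56 = 336.

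**Inputs.** 12 planned infusions and the crediting rule (SAP 6.3.6); 9034 µg/m² cumulative (Protocol 5.1.2); 75% of AG019 doses and one teplizumab dose (SAP 5); 12 patients per combination cohort, the first 2 on open-label active treatment and 10 randomised 4:1 (Protocol 3.3). Assumption: equal daily doses, 9034/12 = 752.8 µg/m² each, because the schedule is redacted.

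**Step 1: compliance against delivered dose.** Let S be infusions started, and f the fraction delivered in an incomplete one.

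- SAP compliance = S/12.
- Delivered share = (complete infusions + sum of f over incomplete infusions)/12.
- Overstatement = sum of (1 − f)/12.

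Each incomplete infusion adds (1 − 0.1)/12 = 7.5 points at f = 0.1, 4.2 at f = 0.5 and 0.8 at f = 0.9. The ceiling is 1/12 = 8.3 points.

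| All 12 started | SAP compliance | Delivered share |
|---|---|---|
| 1 incomplete, f = 0.5 | 100% | 11.5/12 = 95.8% |
| 3 incomplete, f = 0.5 | 100% | 10.5/12 = 87.5% |
| 3 incomplete, f = 0.1 | 100% | 9.3/12 = 77.5% |

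With unequal doses, an infusion carrying share w of the planned total is over-credited by w(1 − f) in dose terms. That may be more or less than the figures above. Day counts would then also differ from dose shares for missed infusions, in either direction.

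**Step 2: what lowers compliance.** An infusion never started scores zero for that day. A patient who stops after one infusion is reported at 1/12 = 8.3%. Only infusions started and not finished are over-credited.

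**Step 3: 6.3.6 beside 6.3.8.** An infusion that was not started is not given in 6.3.6 and withheld in 6.3.8, so the two agree. An infusion started and stopped midway for an adverse event is given in 6.3.6. In 6.3.8 it is withheld if the site recorded teplizumab as interrupted or withdrawn. The sections conflict in that case only, and the SAP does not say how such a stop is coded.

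**Step 4: the two PD-PP bars.**

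- AG019: 0.75 × 336 = 252 capsules.
- Teplizumab: 1/12 = 8.3% of planned infusions. If a partial infusion counts as a dose, which section 5 does not settle, this is 0.8% to 7.5% of planned dose for f = 0.1 to 0.9.
- For scale, 75% of 12 infusions is 9.
- Active patients per combination cohort: 2 + 0.8 × 10 = 10, so one such patient is 10% of the active group.

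**The case against.** Three stronger readings are tempting, and the documents support none of them.

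- **One infusion makes a patient per-protocol.** It does not. The AG019 bar and the deviation clause also apply, and the redacted footnotes may narrow the set further. A large teplizumab shortfall might itself count as a major deviation; that cannot be seen.
- **Exposure is overstated in precisely the patients who could not tolerate teplizumab.** The documents give neither the frequency nor the causes of incomplete infusions. Laboratory values are checked before each infusion, and days withheld as a result, like days after permanent discontinuation, do reduce compliance. The one-dose rule governs set membership and inflates no exposure figure.
- **The safety conclusions are compromised.** TEAE incidence on the safety set does not use the compliance percentage. Individual compliance data and the adverse events linked to infusion withholding are listed.

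It is also fair to say that Protocol 11.4.3.5.1 uses interruption for skipping whole days. On that reading 6.3.6 and 6.3.8 agree, and the wording needs only clarification. The study is descriptive, has no tests, and defines a PD-ITT set.

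These points limit the reach of the problem without removing it. Listings do not correct a summary percentage, and 6.3.6 does not say they will show the amount infused. The PD outputs in section 7.1 name a PD analysis set without saying whether it is PD-ITT or PD-PP, so the presence of PD-ITT results beside PD-PP is not assured. Nothing visible explains the one-dose bar or squares it with Protocol 10.3.3.

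**Conclusion.** The point holds in a limited form, as a change that should be made.

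- **Exposure table:** crediting incomplete infusions in full overstates the delivered amount by up to 8.3 points per incomplete infusion, assuming equal daily doses. The total depends on how many infusions were incomplete, which the documents do not give.
- **Classification:** a conflict between 6.3.6 and 6.3.8 is possible, conditional on how a mid-infusion stop is coded.
- **PD-PP:** the teplizumab bar is 1/12 of planned infusions against 75% for AG019. It is looser than the protocol's PD set and undeclared. It can dilute PD-PP by 10% of the active group per affected patient in a full cohort, subject to the other entry conditions and the redacted footnotes.

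The consequences stay within the descriptive exposure and PD summaries.

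**What to change.** 1. In SAP 6.3.6, tabulate complete, incomplete and not-given infusions per patient and treatment group. Where the infused amount is recorded, add the percentage of planned dose delivered. The documents do not show that it always is, so the counts are the minimum.
2. State how an infusion started and then stopped is classified, and use that classification in both 6.3.6 and 6.3.8.
3. In SAP 5, replace the one-dose condition with a pre-specified, justified minimum share of planned teplizumab or matching-placebo infusions, consistent with Protocol 10.3.3. The SAP's own 75% is one option; the documents do not make it the only one. This is a rule for set membership and changes no treatment decision.
4. Declare the departure from the protocol's PD set in SAP 6.1.

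Fix the threshold before database lock and before the third-interim unblinding, which fits SAP 5 and 6.9. Protocol 10.8 ties the second interim analysis to unblinding of Combination Cohort 1, and SAP 6.9 says that analysis is done. The threshold should therefore be justified without reference to PD results already seen.

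The cost is some SAP wording and a few table rows. PD-PP may be slightly smaller, and reported exposure slightly less favourable.

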6.3.7 Concomitant Medications

All concomitant medications/therapies (including insulin medication) will be classified according to ATC level 3 group text and World Health Organization (WHO) Drug Dictionary preferred name. The medications will be divided into two timing categories based on start date and end date: Prior and Concomitant Medications:

- Prior Medications: start date and end date before first day of IMP
- Concomitant Medications:
 - o Start date before first day of IMP and end date after or on same day as first day of IMP or no end date, i.e. ongoing after first day of IMP; or
 - o Start date after or on same day as first day of IMP

If the date for a concomitant medication is completely missing, it will be assumed that the medication was started before treatment and classified as Prior Medication. If the year and/or month are available, medication start in relation to the first day of IMP will be evaluated as far as possible (e.g., if only the year when the medication was started is available and ongoing is checked, the medication will be classified as a Concomitant Medication). If the medication was started in the same month as the first day of IMP, the medication will be classified as a

Concomitant Medication. Relative day will not be calculated for medications with incomplete dates.

The concomitant medications will be presented in a summary table according to timing in relation to IMP (i.e., Prior and Concomitant). Each subject will only be counted once for each medication and timing category, on a preferred name level.

One list for each timing category (Prior and Concomitant) will be presented.

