Prohibited therapy during the entire treatment period includes any antibiotic treatment known to affect the viability of L. lactis sAGX0407 (see Appendix B), β -cell stimulants, immunosuppressive or immunomodulatory therapies, including systemic steroids, other investigational drug(s), vaccination with live virus or organism, anti-CD3 antibody, any anti-diabetic agents other than insulin, medications known to influence glucose tolerance and daily use of non-steroidal anti-inflammatory agents.

For patients enrolled in the combination cohorts, premedication with ibuprofen or similar non-steroidal anti-inflammatory drugs (NSAID) and with an antihistamine is recommended and may be useful in patients who develop rashes during teplizumab administration.

As paracetamol may induce false positive signals of hyperglycemia by the continuous glucose monitoring devices, its use for reasons other than the reasons mentioned in the previous paragraph should be avoided as much as possible throughout the study.

Confidentiality Statement

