6.6 Handling of Dropouts and Missing Data

The data will be analysed as is except for missing dates for concomitant medication and adverse event, see those sections.

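### The SAP classes medications with a completely missing date as Prior on an assumed early start alone, although its definition of Prior also requires an end before the first IMP day

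*SAP*

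**What the plan says.** SAP 6.3.7 sorts medications into two timing categories. The first has two conditions: "Prior Medications: start date and end date before first day of IMP". A medication is Concomitant if it started on or after the first IMP day. It is also Concomitant if it started earlier and either ended on or after that day or has no end date. The SAP words this last alternative as "or no end date, i.e. ongoing after first day of IMP".

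The section then deals with incomplete dates:

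- Date completely missing: "it will be assumed that the medication was started before treatment and classified as Prior Medication".
- Year only: "if only the year when the medication was started is available and ongoing is checked, the medication will be classified as a Concomitant Medication".
- Same month as first IMP: "If the medication was started in the same month as the first day of IMP, the medication will be classified as a" Concomitant Medication.

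For adverse events, SAP 6.3.8 goes the other way: "If the start date of an AE is missing, it will be assumed that the AE started after the first administration of IMP".

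SAP 6.6 adds no further handling: "The data will be analysed as is except for missing dates for concomitant medication and adverse event", with a pointer back to those two sections.

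Both timing categories are tabulated and listed (SAP 6.3.7; SAP 7.1, item 14.3.10; SAP 7.2, item 16.2.12).

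**The concern.** The missing-date rule fills in one of the two facts that Prior requires and then assigns Prior as if both were known. Nothing is assumed or checked about when the medication ended, or whether it was still being taken. A record can thus carry positive information of on-treatment use, such as an ongoing tick, and still be reported as a medication that was over before treatment.

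What is at stake is the accuracy of the Concomitant table and list. Therapy is recorded from consent onward (Protocol 5.1.4), so pre-treatment and on-treatment drugs come from the same data and only the timing rule separates them. The Concomitant output is where a reader would look for therapies that the protocol rules out on treatment ("Prohibited therapy during the entire treatment period includes any antibiotic treatment" that affects the viability of the bacterium, systemic steroids, immunomodulators and others) and for ongoing insulin, which these tables include.

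**Working it through.** The plan gives no figure to reproduce, and the number of undated medication records is not in the documents. The check is therefore one of logic: take each pattern of dates with the start completely missing, accept the SAP's assumption that the start was before treatment, and compare the category given by the definitions with the one given by the missing-date rule.

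| Pattern (start missing, assumed before IMP) | Definitions in SAP 6.3.7 | Missing-date rule | Result |
|---|---|---|---|
| A. End date known, before first IMP | Prior | Prior | Agree |
| B. End date known, on or after first IMP | Concomitant | Prior, if the rule refers to the start date | Conflict on that reading |
| C. No end date, ongoing checked | Concomitant | Prior | Conflict on any reading |
| D. No end date, ongoing not checked | Concomitant if *no end date* is taken literally; open if the *i.e. ongoing* gloss limits it to confirmed use | Prior | Ambiguous |

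**Which date the rule means.** The SAP does not say whether it refers to the start, the end or both. Its consequence is worded in terms of when the medication started, and the next sentence, on partial dates, also concerns the start. The start date is therefore the natural reading, and under it all four patterns arise. If both dates must be absent, only C and D arise, and C still conflicts.

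**Comparison within the paragraph.** A start year with ongoing checked gives Concomitant. Remove the year, keep the ongoing tick, and the record becomes Prior. Losing the start year says nothing about whether the drug was still in use, so the change of category has no basis in the data.

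**Direction of the other rules.** The year-only example, the same-month rule and the adverse-event rule all resolve doubt towards on-treatment. The completely-missing rule for medications is the only one of the four that goes the other way. As a result, an undated adverse event would count as treatment-emergent while an undated drug given for it would be Prior.

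**Whether another rule corrects it.** SAP 6.6 names only the medication and adverse-event date rules as exceptions to analysing the data as they are. Nothing else moves patterns B or C back to Concomitant.

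**The case against.** The best defence is that the missing-date sentence is a specific rule for records the general definitions cannot place. On that view *no end date* is tied by its own gloss to ongoing use, and an unknown end with ongoing unchecked is simply missing information. This stands for pattern D. A reader might infer that every undated record is misplaced under the SAP's own definitions, and the wording does not support that. The defence does not reach pattern C, where ongoing use is recorded, or pattern B on the start-date reading.

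A second point is that such records should be rare. Start and stop dates must be recorded (Protocol 5.1.4), medications are asked about at every visit (Protocol 6.1), repeat dose patients report changes in an electronic diary (Protocol 6.4.1), and inconsistent data are queried (Protocol 12.3). A fully undated record may well be an old pre-study drug. This stands, and it limits the size of the problem.

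A reader might also infer that prohibited drugs would be hidden. They would not be: a misplaced drug still appears in the Prior table and list, instances of prohibited therapy go to the medical monitor (Protocol 5.1.4), and protocol deviations are listed separately (SAP 7.2, item 16.2.2).

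Nor can an effect on the per-protocol pharmacodynamic set be shown. SAP 5 bases that set on the share of doses received and on major deviations, its footnotes are blacked out, and nothing says that deviations are derived from the Concomitant table.

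Finally, the adverse-event rule serves the primary endpoint and the medication rule does not, so a difference in convention is not in itself an error. That is fair. The case rests on the conflict with the definition of Prior, and the adverse-event rule is only supporting context.

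**Conclusion.** The inconsistency is real and lies within one section. SAP 6.3.7 assigns Prior on the strength of an assumed start, while its definition of Prior also needs an end before first IMP. Undated records marked ongoing are misclassified on any reading. Records with a missing start and an end date on or after first IMP are misclassified if the rule refers to the start date. Records with no end date and no ongoing tick remain ambiguous.

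The impact is low. The number of affected records is unknown and, given the collection requirements, assumed small. It is tempting to express the effect as a share of a group. Each combination cohort has 2 open-label active patients and 10 randomized 4:1, so 2 + 8 = 10 active and 2 placebo, and one patient is 1/10 = 10% or 1/2 = 50%. Those figures only restate the group sizes and would apply to any discrepancy in a single patient; they are not an estimate of this one. The study is descriptive and no test or primary result depends on the rule. What is affected is whether a drug is shown under the right timing heading.

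**What to change.** Replace the completely-missing-date sentence in SAP 6.3.7 with a rule along these lines: *when the start date of a medication is completely missing, the medication is classed as Prior only if a recorded end date, full or partial, shows that it stopped before the first day of IMP; otherwise it is classed as Concomitant.*

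This names the date concerned and leaves pattern A as it is. It brings B and C into line with the definitions and settles D in the same cautious direction as the adverse-event rule. The partial-date rules need no change.

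The cost is one sentence and a small change to the program that assigns the timing category. The downside is some misclassification the other way: a few medications that stopped before the study, with unknown end dates, will appear as Concomitant. A table footnote giving the number of records placed by the rule would show the reader how much it matters. The change should be settled before the blind is broken for the third interim analysis, in keeping with SAP 6.9.

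### SAP 6.3.7: the same-month rule for incomplete start dates ignores a known end date before first IMP, so some Prior medications are classed as Concomitant against the SAP's own definition

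*SAP*

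**What the plan says.** SAP 6.3.7 sets the principle first: "The medications will be divided into two timing categories based on start date and end date: Prior and Concomitant Medications". The categories follow:

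- Prior: "Prior Medications: start date and end date before first day of IMP".
- Concomitant, first limb: "Start date before first day of IMP and end date after or on same day as first day of IMP or no end date".
- Concomitant, second limb: "Start date after or on same day as first day of IMP".

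The next paragraph deals with missing and incomplete dates, in this order:

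- No date at all, assigned to Prior: "If the date for a concomitant medication is completely missing, it will be assumed that the medication was started before treatment and classified as Prior".
- Partial date, to be judged from what is known: "If the year and/or month are available, medication start in relation to the first day of IMP will be evaluated as far as possible". The worked example is a medication with only a start year and the ongoing box ticked, which becomes Concomitant.
- Start in the dosing month, assigned to Concomitant: "If the medication was started in the same month as the first day of IMP, the medication will be classified as a"; the sentence ends by naming that category.
- A closing remark on listings: "Relative day will not be calculated for medications with incomplete dates".

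SAP 6.6 adds that data are taken as recorded, with missing dates for medications and adverse events as the only exceptions. The corresponding adverse event rule in SAP 6.3.8 is expressly confined to start dates that are partially missing.

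**The concern.** The principle uses both dates, but the same-month sentence uses only the start month. Where the start day is missing and a complete end date before first dosing is on file, the two give opposite answers.

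The definition needs no imputation here. A medication that ended before first IMP also started before it, so both conditions for Prior are met. The rule replaces a determined answer with the wrong one.

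At stake is how pre-dose use is displayed. Protocol 5.1.4 has therapy recorded from consent onward, so courses taken during the 28-day screening period enter the data. Protocol 4.3 excludes current use of systemic antibiotics (with exceptions), so a course finished during screening need not bar a patient. Protocol 5.1.4 prohibits antibiotics that affect *L. lactis* viability during treatment. A finished screening course shown as Concomitant would look like use during that period.

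**Working it through.** The plan states no figure to reproduce, so the check applies the SAP 6.3.7 rules to date patterns. Take first IMP on 20 March as an illustration.

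| Recorded start | Recorded end | By the definitions | By the same-month rule, read in context | Conflict |
|---|---|---|---|---|
| 3 March | 10 March | Prior | Not triggered (dates complete) | No |
| March, day unknown | 10 March | Prior (start no later than 10 March) | Concomitant | **Yes** |
| March, day unknown | On or after 20 March | Concomitant under either limb | Concomitant | No |
| March, day unknown | None, or ongoing | Concomitant under either limb | Concomitant | No |
| March, day unknown | March, day unknown | Cannot be determined | Concomitant | No; a cautious default |

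Only the second row fails.

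**How often the month coincides.** Assume a 30-day month, first dosing day D uniform on 1 to 30, and a 28-day screening window (protocol section 4). Let m = min(D − 1, 28) be the number of screening days in the dosing month.

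- Share of medication *starts* in the dosing month: sum of m over D, divided by 30 × 28 = 434/840 = 0.517.
- Share of *completed courses* (start and end both in the window, all pairs equally likely) that start in the dosing month. Each D has 28 × 29/2 = 406 pairs, of which m(m + 1)/2 qualify. Over all D: 4466/(30 × 406) = 4466/12180 = 0.367.
- Enumerating a 365-day calendar year instead gives 0.523 and 0.375.

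For courses finished before dosing, the relevant share is therefore about 37% to 38%, not about half: courses that have already ended tend to have started earlier. It would describe all records only if the rule reached fully dated medications. In context, it can apply only to courses with a missing start day and a known pre-dose end date. The documents do not give their number, so no count of affected records follows.

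**Weight of one record.** Each patient counts once per preferred name and timing category (SAP 6.3.7). An AG019 cohort has 4 to 6 repeat-dose patients (protocol 3.2), so one record can move a cell by 1/6 = 17% to 1/4 = 25%. Each combination cohort randomizes 10 patients 4:1 (protocol 3.3), giving 2 on placebo, where one record moves a cell by 1/2 = 50%.

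**The case against.** A reader who takes the same-month sentence alone might infer that every medication started in the dosing month becomes Concomitant, including fully dated ones, and that about half of completed screening courses would be misplaced. The documents do not support this. The sentence stands between rules for missing and partial dates in a paragraph that closes on incomplete dates, SAP 6.6 confines special date handling to missing dates, and the parallel adverse event rule covers only partial ones. Fully dated medications follow the definitions. This objection stands, although the sentence does not itself state its scope.

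Further points on the other side:

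- **The affected record is unusual.** Protocol 5.1.4 requires start and stop dates, and protocol 6.1 has them collected at every visit. A medication begun in screening with an unknown start day but a known end day should be rare. This stands.
- **Some drug classes should seldom arise.** Protocol 4.3 excludes systemic steroids within 1 month before randomization and use of medications known to influence glucose tolerance. This stands; antibiotics are the better illustration.
- **Other safeguards exist.** The medical monitor is to be told of prohibited therapy (protocol 5.1.4), protocol deviations have their own listing (SAP 7.2), and recorded dates appear in the listings (SAP 6.3.3), so a pre-dose end date would be visible. This stands and limits the consequence.
- **Concomitant is a cautious default.** This stands when the end date is missing, ongoing or itself partial. It does not stand when a known end date rules out use on or after the first day of IMP.
- **A careful programmer could resolve it.** The principle and the instruction to evaluate partial dates as far as possible point to Prior. But the specific sentence says otherwise without exception, and the result should not depend on who programs it.

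**Conclusion.** The point holds in a narrow form. For a medication with an incomplete start date in the month of first IMP and a known end date before first IMP, the same-month rule contradicts the SAP's definition of Prior. This rests on the wording alone and needs no distributional assumption.

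The consequence is minor. It is confined to the Prior and Concomitant medication tables and listings (SAP 6.3.7; outputs 14.3.10 and 16.2.12). The primary endpoint, TEAE incidence up to the 6-month visit, does not use the label. Nor do the analysis sets: as SAP section 5 states them, PD-PP membership depends on doses received and major protocol deviations. The number of affected records is unknown and probably small. The 37% to 38% share rests on uniform dates and is a fraction of that unknown number. The cell shifts of 17% to 50% show what one record could do to a descriptive table, not what is expected.

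**What to change.** Replace the same-month sentence in SAP 6.3.7 with:

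*If the start date is incomplete and the medication was started in the same month as the first day of IMP, it will be classified as Concomitant, unless the end date is known to be before the first day of IMP, in which case it is Prior.*

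This states the scope already implied by the paragraph and SAP 6.6, and keeps the cautious default where the end date is missing, partial or ongoing. The cost is one SAP sentence and one programming condition. No additional data are needed.
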